**Table 2 Criteria for Potentially Clinically Significant Vital Signs and Body Weight**

Vital Sign Parameter	Flag	Criteria a	
		Observed Value	Change from Baseline Value
Systolic blood pressure (mmHg)	High	≥140	Increase of ≥20
	Low	≤90	Decrease of ≥20
Diastolic blood pressure (mmHg)	High	≥90	Increase of ≥15
	Low	≤50	Decrease of ≥15
Heart rate	High	≥100	Increase of ≥15

**Table 2 Criteria for Potentially Clinically Significant Vital Signs and Body Weight**

Vital Sign Parameter	Flag	Criteria a	
		Observed Value	Change from Baseline Value
(beats per minute)	Low	≤45	Decrease of ≥15
Weight (kg)	High	-	Increase of ≥5%
	Low	-	Decrease of ≥5%
Body temperature	High	> 38.3°C or > 100.9°F	
	Low	< 35°C or < 95°F	
Respiratory rate (breaths/min)	High	> 25	
	Low	< 10	

a A post-baseline value is considered as a PCI value if its meets both criteria for observed value and change from baseline. All vital signs data will be listed for the Safety Set.

#### 7.4 Electrocardiogram (ECG)

Descriptive statistics for ECG variables (eg, heart rate, PR interval, RR interval, QRS interval, QT interval, and QTc interval) and their changes from baseline at each assessment time point will be presented by cohort and treatment group. QTc interval will be calculated using both Bazett ( $QTcB=QT/(RR)^{1/2}$ ) and Fridericia ( $QTcF=QT/(RR)^{1/3}$ ) corrections; and if RR is not available, it will be replaced with 60/hr in the correction formula. ECG interpretation will be summarized by visit. A shift table from baseline to each visit for qualitative ECG results will be presented. If the QTcF interval is increased by >45 msec from the baseline, or an absolute QTcF value is >500 msec for any scheduled ECG, then ECG should be repeated 2 more times and the average of the 3 QTc values will be recorded in the CRF and used to generate descriptive summary.

Electrocardiogram variable values will be considered PCS if they meet or exceed the normal limit values listed in Table 3. The number and percentage of subjects with post-baseline PCS values will be tabulated by cohort and treatment group. The percentages will be calculated relative to the number of subjects with available non-PCS baseline and at least 1 post-baseline assessment. The numerator is the total number of subjects with at least 1 PCS post-baseline ECG value. A listing of all subjects with post-baseline PCS value will be provided including the subject number, baseline, and post-baseline PCS values.

**Table 3 Criteria for Potentially Clinically Significant ECG Values**

Parameter	Classification	Criteria
Overall evaluation	ABNORMAL	Overall evaluation is ABNORMAL
Heart rate (bpm)	LOW and DECREASE	$\leq 45$ and decrease of $>15$ from baseline value
	HIGH and INCREASE	$\geq 100$ and increase of $>15$ from baseline value
PR interval (msec)	HIGH and INCREASE	$\geq 200$ and increase of $\geq 20$ from baseline value
QRS interval (msec)	HIGH	$\geq 120$
QTc interval (men) (msec)*	HIGH	$>430$ and increase from baseline value $>30$
QTc interval (women) (msec)*	HIGH	$>450$ and increase from baseline value $>30$

Abbreviations: bpm=beats per minute; QTc=QT interval corrected.

\*Values noted refer to both Bazett's (QTcB) and Fridericia's (QTcF) formula

All ECG results will be presented in data listings.

## 8. PHARMACOKINETIC ANALYSIS

All summaries and analyses of the PK data will be based on the Pharmacokinetic Set defined in Section 4.3.

Each subject's data (eg, dosing records, sample collection records, protocol deviations, etc.) will be reviewed for data exclusion from the descriptive statistics and statistical analysis on a case-by-case basis at the discretion of the pharmacokineticists. Rationale of data exclusion will be provided in a data listing.

Derivations of the PK parameters will be found in the Clinical Pharmacology Analysis Plan.

### 8.1 Drug Concentration

A PK evaluation of maribavir concentrations and [REDACTED] concentrations will be performed based on the PK Set. During this study, blood samples will be drawn from each subject for the determination of plasma concentration of maribavir and [REDACTED]. Serial blood samples will be collected at the following time points.

#### Collection of Blood Samples for Pharmacokinetic Analysis

Cohort	Analyte	Matrix	Dosing Day	Scheduled Time (hours)
A: Non-Hispanic Caucasian subjects	Maribavir and [REDACTED]	Plasma	Day 1 of treatment period 1	Predose, 0.25, 0.5, 1, 1.5, 2, 3, 4, 5, 6, 8, 12, 16, 20, and 24 hours post dose
B: Subjects of Japanese descent	Maribavir and [REDACTED]	Plasma	Day 1 of all 3 treatment periods	Predose, 0.25, 0.5, 1, 1.5, 2, 3, 4, 5, 6, 8, 12, 16, 20, and 24 hours post dose

Plasma concentrations of maribavir and [REDACTED] will be measured using a validated analytical method.

The concentration of plasma maribavir and [REDACTED] will be summarized by cohort, treatment group, and scheduled sampling time using descriptive statistics (n, arithmetic mean, SD, geometric mean median, minimum, and maximum). Individual plasma concentration data will be presented in data listings by cohort and treatment group.

Individual concentrations of plasma maribavir and [REDACTED] will be plotted by actual time on linear and semilogarithmic scales for each subject, displaying all treatments. Plots of mean plasma maribavir and [REDACTED] concentrations versus nominal time for all treatments will also be provided on linear and semilogarithmic scales.

#### 8.1.1 Handling Data with Below Limit of Quantitation (BLQ) Values

The following procedures will be used for plasma maribavir concentrations below the lower limit of quantification (LLOQ):

- Concentrations that are below limit of quantification (BLQ) are reported as <LLOQ on the

06 Aug 2020

data listings, where LLOQ is replaced by the actual LLOQ value for respective PK assay.

- Concentrations that are BLQ are treated as zero in the calculation of summary statistics (eg, mean, SD, etc.) for the plasma concentrations at individual time points. Geometric mean will be set to missing where zero values exist.
- Mean concentrations are reported as zero if all values are BLQ or zero, and no other descriptive statistics are reported. If the calculated mean ( $\pm$  SD) concentration is less than the LLOQ, the value will be reported as calculated. The mean values derived using these conventions will be used to create the mean plasma concentration versus time plots.
- For calculation of PK parameters, BLQ values prior to the first measurable concentration will be set to zero. All BLQ values following the first measurable concentration will be set to “missing”.
- Missing values will not be imputed.

## 8.2 Pharmacokinetic Parameters

A PK evaluation of plasma concentrations of maribavir and [REDACTED] will be performed based on the PK Set. PK parameters will be estimated for maribavir and [REDACTED] following the administration of maribavir 400 mg for non-Hispanic, Caucasian subjects and of maribavir 200, 400, and 800 mg for subjects of Japanese descent.

Maribavir  $C_{max}$ ,  $AUC_{last}$ , and  $AUC_{0-inf}$  will be the primary endpoints. [REDACTED]

PK parameters will include, but not be limited to the following:

- $C_{max}$  Maximum observed plasma concentration
- $t_{max}$  Time of maximum observed concentration sampled during a dosing interval
- $AUC_{last}$  Area under the curve from the time of dosing to the time of last measurable concentration
- $AUC_{0-inf}$  Area under the curve extrapolated to infinity, calculated using the observed value of the last non-zero concentration
- $AUC_{0-inf}^{0/extrap}$  The percent of  $AUC_{0-inf}$  extrapolated, calculated by  $(1 - AUC_{last}/AUC_{0-inf}) * 100$
- $\lambda_z$  Elimination rate in the terminal phase
- $t_{1/2}$  Terminal half-life
- $CL/F$  Apparent total body clearance following extravascular administration calculated as dose divided by  $AUC_{0-inf}$
- $V_z/F$  Apparent volume of distribution following extravascular administration calculated as  $CL/F$  divided by  $\lambda_z$

- $T_{lag}$  Delay between the time of dosing and time of appearance of drug concentration in plasma in the employed sampling scheme

In addition, dose-normalized (to 400 mg)  $AUC_{last}$ ,  $AUC_{0-inf}$ , and  $C_{max}$  will be calculated for Japanese subjects.

Individual plasma PK parameters for maribavir and [REDACTED] will be summarized by cohort and treatment group using descriptive statistics (n, arithmetic mean, SD, median, minimum, maximum, and %CV). In addition, geometric mean, 95% CI of geometric mean and geometric CV% will be computed for original and dose-normalized  $C_{max}$ ,  $AUC_{last}$  and  $AUC_{0-inf}$ . Individual plasma PK parameters will be presented in a data listing for each cohort and treatment group.

Scatter plots of individual plasma  $C_{max}$  and AUCs for maribavir and [REDACTED] versus dose will be provided. Box-Whisker plots for selected dose-normalized PK parameters will be generated with Japanese cohort and Non-Hispanic Caucasian side by side at 400 mg.

### 8.3 Statistical Analysis of Pharmacokinetic Data

In order to compare the PKs of maribavir between subjects of Japanese descent and matched non-Hispanic, Caucasian subjects, the differences of log-transformed PK parameters ( $C_{max}$ ,  $AUC_{last}$ , and  $AUC_{0-inf}$ ) from the maribavir 400 mg oral dose will be examined between cohorts using an analysis of variance (ANOVA) model. The geometric mean ratio and its 90% CI of PK parameters for Japanese descent vs Caucasian will be provided from the model.

In addition, the difference of log-transformed dose-normalized  $C_{max}$ ,  $AUC_{last}$ , and  $AUC_{0-inf}$  will be examined between the following dose groups using an ANOVA model.

- the Japanese cohort estimated at the 200 mg dose and the Non-Hispanic Caucasian cohort estimated at the 400 mg dose
- the Japanese cohort estimated at the 800 mg dose and the Non-Hispanic Caucasian cohort estimated at 400 mg dose

The geometric mean ratio and its 90% CI will be provided from the model. Forest plots of geometric mean ratios for selected PK parameters between Japanese cohort vs the Non-Hispanic Caucasian cohort at 400 mg will be generated.

#### Dose proportionality

Dose proportionality will also be examined for maribavir PK parameters for the Japanese subjects. Dose proportionality will be assessed for  $C_{max}$  and AUC ( $AUC_{last}$  and  $AUC_{0-inf}$ ) using the power model. The power model assumes a linear relationship between the natural log transformed PK parameter and the natural log transformed dose.

$\ln(\text{PK Parameter}) = \alpha + \beta \times \ln(\text{Dose}) + \text{Random error}$

where  $\alpha$  is the intercept,  $\beta$  is the slope, and Random error is a random residual error. Dose proportionality will be assessed by estimating mean slope with the corresponding two-sided 90% CI from the power model. Dose proportionality is concluded when the 90% CIs of the slope  $\beta$  lie entirely within  $(1 + \ln(0.8)/\ln(r), 1 + \ln(1.25)/\ln(r))$ , where  $r$  is a ratio that describes the dose range and is defined as (highest dose/lowest dose). The fold increase in PK parameters and associated 90% CI when doubling the dose will be presented.

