4.5 Discontinuation of Subjects

A subject may withdraw from the study at any time for any reason without prejudice to his/her future medical care by the physician or at the institution, or may be withdrawn at any time at the

discretion of the investigator or sponsor (eg, in the interest of subject safety). The investigator is encouraged to discuss withdrawal of a subject with the medical monitor when possible.

If IP is discontinued, regardless of the reason, the early withdrawal evaluations listed in [Table 1](#) and [Table 5](#) are to be performed as completely as possible. Whenever possible, all discontinued subjects should also undergo follow-up evaluations. Comments (spontaneous or elicited) or complaints made by the subject must be recorded in the source documents. The reason for discontinuation, date of discontinuation of the IP, and the total amount of IP administered must be recorded in the source documents and the case report form (CRF).

Subjects who discontinue early without completing all planned PK assessments for Treatment Period 1 may be replaced at the sponsors discretion to ensure at least 24 subjects (12 subjects of Japanese descent and 12 matching, non-Hispanic, Caucasian subjects) with evaluable PK for the statistical analysis of the primary objective (PK comparison between Japanese and non-Hispanic, Caucasian subjects). If subjects discontinue early during Treatment Period 2 or 3, there is no need for replacement.

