6.2.2 Dosing

The non-Hispanic, Caucasian subjects will receive a single oral dose of 400 mg maribavir (2×200 mg maribavir tablets) on Day 1. The Japanese subjects will receive 3 doses of maribavir: on Day 1 of Treatment Period 1, they will receive a single oral dose of 400 mg of maribavir (2×200 mg maribavir tablets); on Day 1 of Treatment Period 2, they will be randomized to receive a single oral dose of either 200 mg (1×200 mg tablets) or 800 mg of maribavir (4×200 mg maribavir tablets); and on Day 1 of Treatment Period 3, they will receive a single oral dose of whichever dosage they did not receive on Day 1 of Treatment Period 2 (200 mg or 800 mg).

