#### **Treatment Period:**

The non-Hispanic, Caucasian subjects will have one Treatment Period. The Japanese subjects will have Treatment Periods 1, 2, and 3.

- In Treatment Period 1, all study subjects (both Japanese and Caucasian) will receive maribavir as a single 400 mg oral dose.
- Depending upon the randomization assignment on Day 1 of treatment period 2, all subjects of Japanese descent will be dosed in a crossover fashion in Treatment Periods 2 and 3. They will receive a single oral dose of either 200 mg followed by 800 mg maribavir or a single oral dose of 800 mg followed by 200 mg maribavir.

The study design flow chart is presented in [Figure 1](#).

Figure 1 Study Design Flow Chart

\*Washout period of 72 to 73 hours after treatment on Day 1.

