### **3.4 Sample Size and Power Considerations**

The sample size consideration for the primary objective of evaluating the PK profile of maribavir, administered as a single oral dose at 400 mg, between Japanese subjects and matched, healthy, adult, non-Hispanic, Caucasian subjects is based on study feasibility and comparable studies.

A total of 24 subjects (12 subjects of Japanese descent and 12 matched, non-Hispanic, Caucasian subjects) will be targeted to be enrolled in the study.

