### **4.3 Pharmacokinetic Set**

The Pharmacokinetic (PK) Set will consist of subjects who receive at least 1 dose of study drug and have evaluable post-dose maribavir PK data (defined as complete concentration-time profile to obtain meaningful estimates of PK parameters). The PK analyses will be based on this analysis set.

Subjects who do not provide reliable concentration-time profile (in 1 or more periods) may be excluded from PK analysis (for the corresponding treatment period).

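### The dose-proportionality power model has no subject term although each Japanese subject receives all three doses, so its 90% CIs are too wide

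*SAP*

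**What the plan says.** SAP 8.3 (Dose proportionality) regresses the log PK parameter on log dose. It has an intercept α, and β "is the slope, and Random error is a random residual error". The protocol has the same equation in the Synopsis and in Section 8.7.1.1. The SAP adds a decision rule: "Dose proportionality is concluded when the 90% CIs of the slope" β fall wholly between 1 + ln(0.8)/ln(r) and 1 + ln(1.25)/ln(r), with r the ratio of highest to lowest dose. A fold increase for a doubled dose, with its 90% CI, comes from the same fit.

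The design is within-subject. All Japanese subjects take 400 mg in Period 1. After that, "all subjects of Japanese descent will be dosed in a crossover fashion in Treatment Periods 2 and 3" (SAP 3.1), and in Period 3 "they will receive a single oral dose of whichever dosage they did not receive on Day 1 of Treatment Period 2" (Protocol 6.2.2).

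No readable part of either document gives this model a subject effect, a within-subject covariance structure or a degrees-of-freedom method. SAP 14 lists only a change to the safety set. The Clinical Pharmacology Analysis Plan requests period and sequence as data fields but does not use them in this model.

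**The concern.** Dose varies only within subjects, so with complete data each subject's overall exposure level cancels out of the slope. A model with one residual error does not know this. It treats 36 values from 12 people as independent, and its residual variance includes differences between people. The slope estimate stays the same, but its CI is no longer a 90% CI.

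Dose proportionality is a secondary objective, and SAP 8.3 judges it pass or fail on this CI. An interval that is too wide can fail a drug that is truly proportional over 200 to 800 mg, and it overstates the uncertainty in the fold increase.

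**Working it through.** **Inputs.** There are 12 Japanese subjects and three doses each (Protocol 3.1 and 6.2.2), with a two-sided 90% CI and the acceptance rule from SAP 8.3. The documents state no power, CV or CI width for this objective; the sample size "is based on study feasibility and comparable studies" (SAP 3.4). There is therefore no plan figure to reproduce beyond the limits, and every CV below is an assumption.

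**Limits.** r = 800/200 = 4, so the limits are 1 ± ln(1.25)/ln(4) = 1 ± 0.161, that is 0.839 and 1.161.

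**Spread of log dose.** The doses are ln 2 apart, so Sxx = 12 × 2 × (ln 2)² = 11.53.

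**Standard errors.** Let sb² and sw² be the between- and within-subject variances on the log scale, each ln(1 + CV²).
- True variance of the slope, complete data: sw²/11.53.
- As written: the residual variance has expectation sw² + (33/34)·sb² on 34 df (t = 1.691).
- With a subject effect: sw² on 23 df (t = 1.714).
- Ratio of CI widths: (1.691/1.714) × √(1 + 0.97·sb²/sw²). This exceeds 1 once sb²/sw² is above about 0.03.

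**Example, between 30%, within 15%.** sb² = ln(1.09) = 0.0862 and sw² = ln(1.0225) = 0.0223. The width ratio is 0.987 × √(1 + 0.97 × 3.87) = 2.15.

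**Simulation.** At least 100,000 trials per row, complete data, true slope 1. The subject-effect columns use the within-subject analysis on 23 df. With complete data its slope equals the random-intercept slope.

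| Between / within CV | Half-width, as written | Half-width, subject effect | Coverage, as written | Criterion met, as written | Criterion met, subject effect |
|---|---|---|---|---|---|
| 20% / 10% | 0.107 | 0.050 | 99.8% | 87% | 100% |
| 10% / 15% | 0.088 | 0.074 | about 95% | 89% | 94% |
| 20% / 15% | 0.121 | 0.074 | 98.8% | 60% | 94% |
| 30% / 15% | 0.159 | 0.074 | 99.8% | 20% | 94% |
| 20% / 20% | 0.137 | 0.099 | 97.4% | 32% | 70% |
| 30% / 20% | 0.172 | 0.099 | 99.2% | 9% | 70% |
| 10% / 30% | 0.153 | 0.147 | 91.6% | 11% | 16% |
| 30% / 30% | 0.203 | 0.147 | 97.4% | 1% | 16% |

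Coverage with a subject effect is 90% in every row. At 30%/15% the fold-increase CI around 2 is 2^(1 ± 0.159) = 1.79 to 2.23 as written, against 2^(1 ± 0.074) = 1.90 to 2.11.

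**False conclusions.** At the boundary slope 0.839 and within-subject CV 15%, the subject-effect analysis passes 5.0% of trials. The model as written passes 2.6%, 0.6% and 0.1% at between-subject CVs of 10%, 20% and 30%. The subject effect restores the intended error rate and does not loosen it.

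**Ceiling.** Even with an estimated slope of exactly 1, the CI as written cannot fit once the residual SD exceeds (0.161/1.691) × √11.53 = 0.323, a total CV of about 33%. With a subject effect the same ceiling (SD 0.319, CV about 33%) applies to within-subject variability alone.

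**Missing periods.** Protocol 4.5 says "If subjects discontinue early during Treatment Period 2 or 3, there is no need for replacement", and under SAP 4.3 a subject's data "may be excluded from PK analysis (for the corresponding treatment period". If periods are lost at random, neither model is biased (mean slope 0.999 to 1.002 in runs of 3,000 trials). In a hypothetical stress case where the two highest-exposure subjects lack 800 mg data, the mean slope at 30%/15% is 0.944 as written and 0.993 with a random intercept.

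**The case against.** The SAP prints a one-line generic model and speaks of a mean slope. It does not specify ordinary least squares, and a programmer might add a subject effect by habit. The error is conservative, the objective is secondary, and the pass/fail limits appear only in the SAP. Dose-normalized summaries and ratios are also reported, and the protocol cites earlier evidence of proportionality. Where between-subject CV is well below within-subject CV the loss is small: at 10%/30%, 11% against 16%. The missing-data bias needs an exposure-related loss that nothing in the documents suggests. A random intercept alone also assumes a common slope. If slopes vary between subjects with an assumed SD of 0.10, its coverage at 30%/15% is about 87%.

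Most of this stands as a limit on size. It does not remove the defect: the printed equation and its definitions contain no random effect, so following them literally gives the wrong CI. If a subject effect is intended, the SAP should state it. The slope-variation point is a good reason to prespecify the random-effects structure. The stress case is only an illustration and carries no weight in the conclusion.

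**Conclusion.** The concern holds. As written, the 90% CIs for the slope and the fold increase are too wide for any realistic between-subject variability. Over assumed CVs of 10% to 50% between and 10% to 30% within, the width ratio runs from 1.04 to 4.71 and actual coverage from about 92% to nearly 100%. The cost in concluding proportionality ranges from a few percentage points to most of the power, depending on CVs the documents do not give. At within-subject CVs of 25% to 30% even the corrected model meets the criterion in only 39% to 16% of trials, so there the 12 subjects are the main limit. With complete data the slope estimate is unchanged. This should be fixed, but it does not threaten the primary comparison.

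**What to change.** Amend SAP 8.3 before database lock, and align the protocol Synopsis and Section 8.7.1.1 if the protocol is amended. For subject i at dose j, specify ln(PK_ij) = α + a_i + β·ln(Dose_ij) + e_ij, with a_i a random subject intercept, fitted by REML with Kenward-Roger degrees of freedom. Take the 90% CIs for β and for 2^β from this model and keep the acceptance limits. State the random-effects structure explicitly, and consider a prespecified sensitivity analysis that lets slopes vary between subjects.

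With six subjects per sequence and complete data, β rests on 800 against 200 mg, which are balanced over Periods 2 and 3, so the point estimate needs no period term. SAP 3.2 states 1:1 randomization but does not guarantee a 6:6 split, so the amendment should say what is done if the split is unequal or data are missing.

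The cost is a few lines of SAP text and a small change to the model code, with no new data.

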- Safety and tolerability will be determined through assessment of TEAEs from the first dose to the post-treatment follow-up telephone call at 7 (± 4) days after the last dose of IP, and vital signs, ECG, and clinical laboratory evaluations on Day 1 pre-dose and up to 24 hours post dose in each treatment period.

Follow-up

- A post-treatment follow-up telephone call will occur at 7 (± 4) days after the last dose of IP for each subject. Subjects who experience AEs will be followed longer if needed, including an unscheduled clinic visit if appropriate, depending on the nature, severity, and seriousness of the AE.

[figure not shown]
Rationale for Study Design and Dose Selection

- Maribavir 400 mg BID is the clinical dose currently being evaluated in the ongoing pivotal Phase 3 studies; therefore, a single oral dose of 400 mg maribavir was selected for evaluating the primary objective of this study – to compare maribavir PK between Japanese and Caucasian subjects. Maribavir has demonstrated time-independent PK and a favorable safety profile in previous Phase 1 studies. Therefore, evaluating PK following repeated dosing, eg, 400 mg BID, is not necessary in this study. Although dose proportionality of PK for doses from 50 mg up to 900 mg was demonstrated in previous studies in Caucasian subjects, to explore the appropriate clinical dosage in Japanese subjects the lower and higher dosages were also selected to assess dose proportionality and to support the future Phase 3 clinical

development of maribavir in Japanese subjects. Therefore, the secondary objective of the study was to evaluate dose proportionality of maribavir PK in subjects of Japanese descent. The doses of 200, 400, and 800 mg were selected for evaluating dose proportionality as a more than two-fold differences in systemic exposure to maribavir is not expected in Japanese subjects as compared to Caucasian subjects. As the primary objective is to compare maribavir PK at 400 mg, the 400 mg dose is to be evaluated in Treatment Period 1 in both Japanese and Caucasian subjects to avoid treatment period effects on this comparison.

Figure 1 Study Design Flow Chart

This is an open-label study to evaluate the PK, safety, and tolerability of single doses of maribavir in healthy, adult subjects of Japanese descent and matched, healthy, adult, non-Hispanic, Caucasian subjects. These cohorts of healthy, non-Hispanic, Caucasian subjects and healthy Japanese subjects need not be dosed at the same time.

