Dose proportionality will also be examined for maribavir PK parameters for the Japanese subjects. Dose proportionality will be assessed for C_{max} and AUC (AUC_{last} and AUC_{0-inf}) using the power model. The power model assumes a linear relationship between the natural log transformed parameter and the natural log transformed dose.

$$\ln(\text{Parameter}) = \alpha + \beta \times \ln(\text{Dose}) + \text{Random error}$$

Where α is the intercept, β is the slope, and Random error is a random residual error. Dose proportionality will be assessed by estimating mean slope with the corresponding two-sided 90% CI from the power model. The fold increase in PK parameters and associated 90% CI when doubling the dose will be presented. [REDACTED]

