### **3.2 Randomization**

Subjects of Japanese descent who meet all the inclusion criteria and none of the exclusion criteria will be randomized (1:1 ratio) to either maribavir 200 mg or 800 mg on Day 1 in treatment period 2. Subjects will then be dosed in a crossover fashion with a single dose of maribavir based on their randomization assignment on Day 1 in Treatment Periods 2, and 3. There is no stratification for this study.

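### The power model omits period (and subject and sequence) although 200 and 800 mg are crossed over Periods 2 and 3; once subject is added, a period shift still widens the slope CI and, if the sequences end unequal, biases the slope

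*SAP*

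**What the plan says.** The secondary objective is dose proportionality over 200, 400 and 800 mg in 12 Japanese subjects.

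- **Design.** SAP 3.1 states: "In Treatment Period 1, all study subjects (both Japanese and Caucasian) will receive maribavir as a single 400 mg oral dose". Then "all subjects of Japanese descent will be dosed in a crossover fashion in Treatment Periods 2 and 3", the order being "either 200 mg followed by 800 mg maribavir or a single oral dose of 800 mg followed by 200 mg maribavir". SAP 3.2 gives a 1:1 ratio and adds: "There is no stratification for this study". No block size appears in either document.
- **Model.** SAP 8.3 and protocol 8.7.1.1 give the same equation: ln(parameter) = α + β ln(dose) + error, where, in the protocol's words, "Random error is a random residual error". Neither lists period, sequence or subject. SAP section 14 records no change to this.
- **Decision rule.** "Dose proportionality will be assessed by estimating mean slope with the corresponding two-sided 90% CI from the power model". Proportionality is concluded if that interval lies inside limits set by r, which "is a ratio that describes the dose range and is defined as (highest dose/lowest dose").
- **Period effects elsewhere.** Protocol 3.1 puts 400 mg first in both cohorts "to avoid treatment period effects on this comparison", meaning the Japanese versus Caucasian comparison.
- **Balance.** Protocol 4.5 does not require replacement of dropouts in Period 2 or 3. SAP 4.3 allows a subject's profile to be excluded for a single period.
- **Data.** The Clinical Pharmacology Analysis Plan (Table 6) asks for dosing period and dosing sequence in the transfer file, but no model uses them.

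**The concern.** The order of 200 and 800 mg is the only randomised element of the trial. Randomising it allows a Period 2 to Period 3 difference to be separated from dose, and the stated model does not make that separation. A subject term alone would not do so either, because a shift between periods occurs within subjects.

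Two consequences follow. The shift enters the residual and widens the interval that is compared with fixed limits. If one sequence contributes more profiles than the other, part of the shift is also read as dose effect. The result is a pass or fail on a secondary objective, in a study meant to guide dose selection for a later Phase 3 trial.

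**Working it through.** **Acceptance limits.** With r = 800/200 = 4: 1 + ln(0.8)/ln 4 = 0.839 and 1 + ln(1.25)/ln 4 = 1.161, so the margin is 0.161. The plan states no SD, power or CI width for the slope, so there is no planned figure to reproduce.

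**Assumptions, none from the documents.** Within-subject SD 0.15 log units; between-subject SD 0.30 (needed only for the model as written); a shift δ that affects Period 3 only; true slope 1; 12 subjects with complete data.

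**Design.** Put x = ln(dose/400). Then x = 0 in Period 1 and -ln 2 or +ln 2 in Periods 2 and 3. The sum of squares of x is 24 x (ln 2)² = 11.53, with root 3.396. Because 400 mg lies at the centre of the ln-dose range, it has no leverage on the slope with or without a period term.

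**Bias without period.** With nA subjects on 200 then 800 mg and nB on the reverse, bias = δ x (nA-nB)/12/ln 4.
- 6:6: zero.
- 7:5, δ = 0.10: 0.10 x 2/12/1.386 = 0.012, or 7% of the margin.
- 8:4, δ = 0.10: 0.10 x 4/12/1.386 = 0.024, or 15%.
- 8:4, δ = 0.20: 0.048, or 30%.

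With period fitted the bias is zero at each of these splits.

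**Dropout from a 6:6 start.** Take two Period 3 profiles lost from one sequence and Period 3 exposure 20% above Period 2. The bias is -0.017 in the model as written and -0.025 with subject fitted. It is zero once period is fitted.

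**CI half-width at 6:6, subject term present.**
- With period (21 df): 1.721 x 0.15/3.396 = 0.0760, whatever δ is.
- Without period (23 df) the expected residual variance is 0.0225 + 12 x (2/3) x δ²/23.
  - δ = 0: 1.714 x 0.15/3.396 = 0.0757.
  - δ = 0.10: 1.714 x √0.02598/3.396 = 0.0813.
  - δ = 0.20: 1.714 x √0.03641/3.396 = 0.0963.

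Simulated averages are about 1% lower: 0.075 with period, and 0.080 and 0.095 without it for δ = 0.10 and 0.20. At δ = 0.20 and 6:6, the simulated chance of concluding proportionality is 85% without period and 94% with it.

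**CI half-width at 6:6, model exactly as written (34 df).** The expected residual sum of squares is 11 x (0.0225 + 3 x 0.09) + 23 x 0.0225 + 8δ² = 3.735 + 8δ².
- δ = 0: 1.691 x √(3.735/34)/3.396 = 0.165.
- δ = 0.10: 0.167 (+1%).
- δ = 0.20: 0.172 (+4%).
- Period added without subject (32 df): 1.694 x √(3.690/32)/3.396 = 0.169. This is wider than 0.167 at δ = 0.10 and barely narrower than 0.172 at δ = 0.20.

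Adding subject takes 0.165 to about 0.076, so the subject term dominates.

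**Cost of the period term when there is no shift.** At 6:6 the half-width goes from 0.0757 to 0.0760, under half a percent. At 8:4 it grows by √(1/(1-(4/12)²)) = √(9/8) = 1.06, or 6%.

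**The case against.** The strongest reply is that a large period effect is unlikely here. Subjects stay in the unit throughout, with doses 72 to 73 hours apart, identical Day 1 meals, a 10-hour fast and a fixed water volume. Protocol 1.2.3 reports time-independent PK and a half-life of 5 to 7 hours, so the washout spans 72/7 = 10 to 72/5 = 14 half-lives and carry-over is negligible. This stands as an argument about size: a shift of 0.20 belongs at the upper end. It does not exclude other period effects, which the protocol guards against in the cohort comparison despite the same PK statement.

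A reader might also infer three stronger things that the documents do not support.

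- *That the sequences will probably be unequal.* Unrestricted allocation of 12 subjects would give exactly 6:6 only C(12,6)/2¹² = 924/4096 = 23% of the time. But SAP 3.2 states a 1:1 ratio and protocol 6.2.1 a randomisation schedule. Silence on blocks is not evidence of unrestricted allocation, and no stratification does not mean no blocking.
- *That the randomised order is wasted.* At 6:6 it already protects the slope estimate without a period term.
- *That the widening from 0.075 to 0.080 or 0.095 describes the SAP's own model.* Those figures assume a subject term that the SAP lacks.

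It may also be said that fitting period discards the 400 mg data. This has little force, because those data have no leverage on the slope under either model when data are complete. It is true that curvature at 400 mg cannot then be separated from a Period 1 effect. That limit comes from the design and should be stated.

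**Conclusion.** The point holds, at modest size. The power model lacks the period, sequence and subject terms that the crossover calls for. With subject added and an assumed within-subject SD of 0.15, omitting period under a 0.10 shift costs about 7% in CI width at 6:6 (0.080 against 0.075). The bias of 0.012 at 7:5 or 0.024 at 8:4 needs both a real shift and unequal sequences, whether from dropout, excluded profiles or an unblocked schedule. The 0.20 case (0.095 against 0.075; 85% against 94% chance of concluding proportionality at 6:6) is an upper bound for illustration, not an expectation.

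It would be wrong to conclude that the slope is biased as planned, or that period is the main weakness of the model. As written, the missing subject term governs the CI width and a period shift adds only 1% to 4%. All sizes depend on SDs and shifts that the documents do not give.

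**What to change.** In SAP 8.3, fit ln(PK parameter) on ln(dose) with period (three levels) and sequence as fixed effects and subject as a random effect. Do not add period without subject. State two consequences: with complete data the slope is estimated from the randomised Period 2/3 contrast, and curvature at 400 mg cannot be separated from a Period 1 effect. Record the change in SAP section 14, since protocol 8.7.1.1 gives the simpler model. A sentence in SAP 3.2 on whether the schedule is balanced would settle the question of initial balance.

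The period term costs two residual degrees of freedom. If there is no period effect, the interval is essentially unchanged at 6:6 and about 6% wider at 8:4. No new data are needed, because period and sequence are already in the planned transfer file. The change should be made before the data are seen, since a period term added afterwards would be open to challenge.
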